## 6.8. Appendix 8 Adverse Events of Special Interest

The following adverse events of special interest will be used for selexipag. These are based on the important identified and potential risks in the latest Risk Management Plan and on-going discussion with Pharmacovigilance Risk Assessment Committee.

AE Special Interest Category
Anaemia
Bleeding events
Gastrointestinal disturbances denoting intestinal intussusception (manifested as ileus or obstruction)
Hyperthyroidism
Hypotension
Light-dependent non-melanoma skin malignancies
Major adverse cardiovascular events (MACE)
Medication errors
Ophthalmological effects associated to retinal vascular system
Pregnancy
Pulmonary venoocclusive disease associated with pulmonary oedema
Renal function impairment / acute renal failure
Prostacyclin associated reactions*

\*Prostacyclin associated reactions will be summarized separate from other AESIs

A specific file containing all preferred terms for each category as per last coding version will be maintained.

## 6.9. Appendix 9 Medications of Special Interest

Concomitant medications of special interest are defined as follows:

Concomitant/Prior Medication Special Interest Category	Standard ATC Name	Note
PAH-specific medications	Sildenafil	Medications with ATC name containing any of the listed standard ATC names are considered as PAH-specific medications.
PAH-specific medications	Tadalafil	
PAH-specific medications	Vardenafil	
PAH-specific medications	Iloprost	
PAH-specific medications	Epoprostenol	
PAH-specific medications	Beraprost	
PAH-specific medications	Treprostинil	
PAH-specific medications	Selexipag	
PAH-specific medications	Riociguat	
PAH-specific medications	Macitentan	
PAH-specific medications	Bosentan	
PAH-specific medications	Ambrisentan	

## 6.10. Appendix 10 Laboratory Toxicity Grading

The grading scale use for lab assessments is based on the tables below.

Blood chemistry marked abnormalities (SI Units)				
Laboratory test name (CDISC Synonym[s])	LL	LLL	HH	HHH
Alanine aminotransferase	NA	NA	$> 3 \times \text{ULN}$	$> 5 \times \text{ULN}$
Aspartate aminotransferase	NA	NA	$> 3 \times \text{ULN}$	$> 5 \times \text{ULN}$
Alkaline phosphatase	NA	NA	$> 2.5 \times \text{ULN}$	$> 5 \times \text{ULN}$
Bilirubin; Total bilirubin	NA	NA	$> 2 \times \text{ULN}$	$> 5 \times \text{ULN}$
Creatinine	NA	NA	$> 1.5 \times \text{ULN}$	$> 3 \times \text{ULN}$
Sodium	NA	$< 130 \text{ mmol/L}$	$> 150 \text{ mmol/L}$	$> 155 \text{ mmol/L}$
Potassium	$< 3.2 \text{ mmol/L}$	$< 3.0 \text{ mmol/L}$	$> 5.5 \text{ mmol/L}$	$> 6.0 \text{ mmol/L}$

CDISC=Clinical Data Interchange Standards Consortium; NA = not applicable; ULN = upper limit of normal.

Blood chemistry marked abnormalities (SI Units)				
Laboratory test name (CDISC Synonym[s])	LL	LLL	HH	HHH
Hemoglobin	$< 100 \text{ g/L}$	$< 80 \text{ g/L}$	$> 20 \text{ g/L}$ above baseline	$> 40 \text{ g/L}$ above baseline
Hematocrit; EVF; PCV (male)	$< 0.32 \text{ L/L}$	$< 0.20 \text{ L/L}$	$> 0.60 \text{ L/L}$	$> 0.65 \text{ L/L}$
Hematocrit; EVF; PCV (female)	$< 0.28 \text{ L/L}$	$< 0.20 \text{ L/L}$	$> 0.55 \text{ L/L}$	$> 0.65 \text{ L/L}$
Platelets (assuming no platelet cluster)	$< 75 \times 10^9/\text{L}$	$< 50 \times 10^9/\text{L}$	$> 600 \times 10^9/\text{L}$	$> 999 \times 10^9/\text{L}$
Leukocytes; white blood cells	$< 3.0 \times 10^9/\text{L}$	$< 2.0 \times 10^9/\text{L}$	$> 20.0 \times 10^9/\text{L}$	$> 100.0 \times 10^9/\text{L}$
Neutrophils (Abs)	$< 1.5 \times 10^9/\text{L}$	$< 1.0 \times 10^9/\text{L}$	NA	NA
Eosinophils (Abs)	NA	NA	$> 5.0 \times 10^9/\text{L}$	NA
Lymphocytes (Abs)	$< 0.8 \times 10^9/\text{L}$	$< 0.5 \times 10^9/\text{L}$	$> 4.0 \times 10^9/\text{L}$	$> 20 \times 10^9/\text{L}$

CDISC=Clinical Data Interchange Standards Consortium; EVF = erythrocyte volume fraction; NA = not applicable; PCV = packed cell volume.

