16.1 Criterion modified per Amendment 3
16.2 Known and documented severe hepatic impairment (with or without cirrhosis) at screening, defined as Child-Pugh Class C^c.
17. Known or suspected uncontrolled thyroid disease (hypo- or hyperthyroidism).
18. Criterion modified per Amendment 3
18.1 Any hospitalization within 10 weeks (70 days) prior to Day 1, inclusive (except elective hospitalizations for surgery or standard monitoring of pre-existing conditions that did not worsen).

^b Pulmonary function tests may be performed either with or without the use of bronchodilators, as per local clinical practice.

^c The assessment of hepatic impairment (Child-Pugh Score) must be fully documented for participants who have clinical signs and/or evidence (from central and/or local lab) of hepatic impairment. Absence of hepatic impairment must be documented in the source data as well.

19. Concomitant life-threatening disease with a life expectancy of less than 12 months.
20. Criterion modified per Amendment 3
 - 20.1 Hemoglobin <80 g/L (<8 g/dL; <4.96 mmol/L) at screening.
21. Hypersensitivity to selexipag or any study intervention excipient (mannitol, maize starch, hydroxypropylcellulose, magnesium stearate, hypromellose, propylene glycol, titanium dioxide, carnauba wax, iron oxide red, iron oxide yellow, iron oxide black).
22. Criterion modified per Amendment 2
 - 22.1 Pregnancy, breastfeeding, or intention to become pregnant during the study.
23. Any factor or condition likely to affect compliance with study intervention or visit plan, as judged by the investigator.
24. Claustrophobia.
25. MRI-incompatible permanent cardiac pacemaker, automatic internal cardioverter.
26. Metallic implant (eg, defibrillator, neurostimulator, hearing aid, permanent use of infusion device, dental brace, metal-containing tattoo ink)^d.
27. Criterion modified per Amendment 3
 - 27.1
 - Cardiac arrhythmia assessed severe by the investigator
 - Conditions that could interfere with proper cardiac gating, eg, atrial fibrillation, multiple premature ventricular or atrial contractions.

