### **5.1.3. Baseline**

Baseline is defined as the last observation on or before the day of the first dose of study intervention. Participants without a baseline value will be excluded from the corresponding analysis.

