### **5.6.4. Additional Safety Assessments**

#### **5.6.4.1. Clinical Laboratory Tests**

Clinical laboratory tests will be displayed for the participants included in the safety analysis set.

Descriptive statistics (observed values and absolute changes from baseline) will be presented for all chemistry and hematology laboratory tests at scheduled time points. All recorded assessments up to EOT + 3 days will be assigned to the most appropriate visit time point according to the best fitting time window for that assessment.

Scatter plots (eDISH plot) of maximum treatment-emergent ALT and AST versus maximum treatment-emergent total bilirubin up to EOT + 3 days will be presented.

An abnormality (abnormality based on criteria defined in tables in Appendix 10, Section [6.10](#)) will be attributed to the baseline and post baseline values.

Post baseline abnormalities will be compared with their corresponding baseline result:

- Treatment-emergent (TE) will be concluded if the post baseline value is worse than the baseline value.
- If the post baseline value is above the upper limit and the baseline value is below the upper limit (e.g., Normal or Low), then the post baseline abnormality will be considered TE. The same applies to the post baseline value being below the lower limit with the baseline value being above the lower limit (e.g., Normal or High).
- If the baseline value is missing, a post baseline abnormality will always be considered as TE.

Treatment-emergent marked laboratory abnormalities (see Section 6.10) will be summarized for each laboratory variable for which marked abnormalities are defined providing their incidence and frequency.

All laboratory data will be listed together with derived marked abnormality flag. A separate listing of all laboratory data for the subjects with at least one marked abnormality value will be provided.

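### SAP Appendix 10 grades hemoglobin marked high on a rise from baseline alone, so recovery from an anemia allowed at entry can be tabulated as a marked high abnormality

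*SAP*

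**What the plan says.** The hemoglobin row of SAP Appendix 10 (6.10) has fixed low limits, LL below 100 g/L and LLL below 80 g/L. Its high limits are changes: HH is "> 20 \text{ g/L}$ above baseline" and HHH is "> 40 \text{ g/L}$ above baseline". Every other high limit given in the two tables is a multiple of the ULN or a fixed value. Hematocrit, for example, is HH above 0.60 L/L in men and above 0.55 L/L in women.

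SAP 5.6.4.1 grades both baseline and post-baseline values, with the "abnormality based on criteria defined in tables in Appendix 10". It then decides treatment emergence. The general rule is "Treatment-emergent (TE) will be concluded if the post baseline value is worse than the baseline value". A second rule covers a change of direction and begins "If the post baseline value is above the upper limit and the baseline value is below the upper limit (e.g., Normal or Low"; such a shift counts as treatment-emergent. SAP 5.1.3 fixes the reference value: "Baseline is defined as the last observation on or before the day of the first dose of study intervention".

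The entry floor is in Protocol 5.2, criterion 20.1, which excludes only "Hemoglobin <80 g/L (<8 g/dL; <4.96 mmol/L) at screening".

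Treatment-emergent marked laboratory abnormalities are a secondary safety endpoint (Protocol 3, SAP 1.1). After early termination efficacy is reduced to listings, but SAP 5.1 keeps the standard safety tables, so this incidence table will still be produced.

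**The concern.** A marked high flag should identify a value that is high. Here it identifies a value that has risen, wherever it started. The protocol lets in participants whose hemoglobin the same table already calls marked low, so their recovery can be flagged as an abnormality in the opposite direction.

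Hemoglobin matters for safety with this drug: anemia is an adverse event of special interest (SAP Appendix 8), and Protocol 2.3.2 reports a small fall in hemoglobin on treatment. A hemoglobin-high row that mixes truly high values with corrected anemia would misstate direction in a secondary safety endpoint. Neither document has a clause exempting a rise that stays within the normal range or corrects a low baseline.

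**Working it through.** The plan states no figure on this point, so there is none to reproduce. The check applies the rule as written.

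**Inputs.** HH if post-baseline minus baseline exceeds 20 g/L, and HHH if it exceeds 40 g/L; LL below 100 g/L and LLL below 80 g/L (SAP Appendix 10). Entry floor 80 g/L (Protocol 5.2), taking the screening value as the baseline. The documents give no hemoglobin ULN; I assume 150 to 180 g/L.

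**Thresholds.** HH starts above baseline + 20, HHH above baseline + 40.

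| Baseline (g/L) | Baseline grade | HH above | HHH above | Example |
|---|---|---|---|---|
| 80 | LL | 100 | 120 | 80 to 101 is HH; 80 to 121 is HHH |
| 90 | LL | 110 | 130 | 90 to 111 is HH |
| 99 | LL | 119 | 139 | 99 to 120 is HH; 99 to 140 is HHH |

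For a baseline of 80 g/L, values below 100 are marked low and values above 100 are marked high. Only exactly 100 g/L carries no flag.

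**All low-entry cases.** Baselines 80 to 99 and rises 21 to 40 g/L in whole numbers give 20 × 20 = 400 pairs. As written, 400 of 400 are HH. The highest value reached is 99 + 40 = 139 g/L. If the value must also exceed the ULN, 0 of 400 are flagged at each assumed ULN of 150, 160, 170 and 180 g/L.

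**Normal baselines.** A rise above 20 g/L can end at or below the ULN whenever baseline is below ULN − 20: below 150 − 20 = 130 g/L at the lowest assumed ULN, and below 180 − 20 = 160 g/L at the highest. For example, 110 to 131 g/L is HH.

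**Treatment emergence.** Baseline minus itself is 0, so a baseline can never be HH and any post-baseline HH is a new grade. For 80 to 101 g/L the Appendix 10 grades go from low to high. If *upper limit* in 5.6.4.1 means the Appendix 10 limit, the second rule makes this treatment-emergent. If it means the laboratory ULN, 101 g/L does not meet that rule. The first rule depends on whether 101 is *worse* than 80, which the SAP does not say.

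**Comparison with hematocrit.** Assume a hemoglobin to hematocrit ratio of 320 to 360 g/L. Then 101 g/L corresponds to 101/360 = 0.28 up to 101/320 = 0.316 L/L, below the male LL limit of 0.32. One male sample could be marked high on hemoglobin and marked low on hematocrit. The hematocrit HH limits correspond to hemoglobin of about 0.55 × 320 = 176 up to 0.60 × 360 = 216 g/L.

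**Effect on the table.** One such case moves the row's incidence by 1/N. The documents do not give the size of the safety set; for assumed N of 5, 10 and 20 the shift is 20, 10 and 5 percentage points.

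**The case against.** The strongest objection concerns treatment emergence. A reader might infer that every HH is automatically treatment-emergent, because baseline can never be HH. The documents do not support that. One rule in 5.6.4.1 needs a worse value, and 85 to 106 g/L is not obviously worse. The other needs a value above an upper limit, and if that is the laboratory range, 106 g/L fails. This stands: the count is the natural reading, because grades are assigned from Appendix 10, but it is not certain. It does not rescue the row, since the sample is still graded marked high and two programmers could produce different tables.

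A reader might also see a conflict with "If the baseline value is missing, a post baseline abnormality will always be considered as TE", since without a baseline no high hemoglobin can be graded. In practice this case hardly arises. Criterion 20.1 needs a screening hemoglobin, Protocol 5 allows no waivers, and local results used for eligibility must be entered in the eCRF. A dosed participant without a baseline value implies an eligibility violation or lost data.

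The different rules for hemoglobin and hematocrit are not in themselves a contradiction. One row flags a large change, the other a level, and Protocol 9.4.5 takes the definitions from sponsor guidelines that are not reproduced. A change criterion is a legitimate choice. The fault is using it alone to define a high value.

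Finally, the practical effect is limited, and this stands too. A false flag needs a rise above 20 g/L on a drug described as slightly lowering hemoglobin, with three planned hematology samples per participant including screening (Protocol 8, Table 3). SAP 5.6.4.1 lists all laboratory data with the flag, and separately all data for anyone flagged, so a reader could see what happened.

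**Conclusion.** The concern holds as a definite but minor error in the grading rule. As written, Appendix 10 flags a recovery of more than 20 g/L from a permitted low baseline as marked high, although the value may still be within or below the normal range. All 400 low-entry cases examined are affected, and none would be if a value above the ULN were also required.

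That these cases reach the treatment-emergent table follows from the natural reading of SAP 5.6.4.1, not from explicit text. The grading result rests only on the documents' cut-offs and the entry floor. The statement that the flagged values are not high rests on the assumed ULN of 150 to 180 g/L, and the percentage shifts rest on assumed values of N.

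The documents give no indication of how often such a rise would occur. With a descriptive analysis, very few participants and full listings, the expected effect on the results is small.

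**What to change.** In SAP Appendix 10, change hemoglobin HH to *more than 20 g/L above baseline and above ULN*, and HHH to *more than 40 g/L above baseline and above ULN*. In 5.6.4.1, add that for this row being above the upper limit means meeting both conditions.

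The cost is two table cells and one sentence; ULN is already needed for five chemistry rows. Large rises that stay at or below the ULN lose the flag but remain in the full laboratory listing. A high value that rose by 20 g/L or less, such as 175 to 190 g/L, is unflagged now and stays so.

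Measuring the excess from the ULN instead, as more than 20 g/L above ULN, would be a poorer remedy because it drops truly high values between ULN and ULN + 20. With an assumed ULN of 160 g/L, 140 to 175 g/L would go unflagged because the threshold becomes 180 g/L. The two-condition rule keeps it: the rise is 35 g/L and 175 exceeds 160.
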